12.2.3 Urinalysis

Numeric urinalysis parameters (pH, specific gravity) will be summarized by descriptive statistics for all scheduled collection times (Baseline, Day 3, Day 8). Categorical urinalysis parameters (Ketones, Protein, Glucose, Bilirubin, Nitrite, Urobilinogen, Occult Blood, Color) will be summarized in the form of shift table. Results of normality (Normal, Abnormal/NCS, and Abnormal/CS) will be summarized for all scheduled collection times.

Numeric and categorical parameters will be listed in separate listings. Both test result will be listed for each subject by actual treatment group, visit and individual test results.

If microscopic examination of sediment performed, the results will be listed.

12.3 Vital Signs

Vital signs of SBP, DBP, heart rate, respiratory rate, and body temperature will be summarized by actual treatment group, at each scheduled collection time (Baseline, Day 2, Day 3, Day 5, Day 8, and Day 110/EOS) using descriptive statistics. Changes from baseline will also be summarized by actual treatment group. Vital sign parameters with body temperature will be listed for each subject by actual treatment group, visit and individual test results.

12.4 Immediate Hypersensitivity

Vital sign parameters (SBP, DBP, respiratory rate, heart rate), body temperature and ECG measured for immediate hypersensitivity on Day 1 will be summarized by treatment group, at each scheduled collection time:

- Vital sign
 - Pre-infusion (within 15 minutes prior to the beginning of the infusion)
 - 30 minutes (± 15 minutes) after the beginning of the infusion
 - Within 15 minutes after the end of the infusion
 - 1 hour (± 15 minutes) after the end of the infusion

Statistical Analysis Plan

- 2 hours (± 15 minutes) after the end of the infusion
- ECG
 - 1 hour (± 15 minutes) after the end of the infusion

Immediate hypersensitivity findings will be classified as “Normal”, “Abnormal, NCS”, and “Abnormal, CS”. The results will be summarized by time point and actual treatment group with the number and percentage of subjects in each classification. The number and percentage of subjects who have a clinically notable vital sign and body temperature will be presented by actual treatment group, time point and parameter. The criteria for clinically notable results are defined as follows:

Parameter:

- SBP (mmHg): Low ≤ 90 , High ≥ 160
- DBP (mmHg): Low ≤ 50 , High ≥ 90
- Respiratory rate (breaths per minute): Low ≤ 12 , High ≥ 20
- Heart rate (beats per minute): Low ≤ 50 , High ≥ 100
- Body temperature ($^{\circ}\text{C}$): Low ≤ 35.0 , High ≥ 38.0

Data collected on monitoring for immediate hypersensitivity; vital sign, body temperature and ECG data will be listed by actual treatment group and time point.

12.5 Electrocardiogram

12-Lead ECG will be performed at screening, on Day 8, and Day 110/EOS. ECG findings will be classified as “Normal”, “Abnormal, NCS”, “Abnormal, CS”. The number and percentage of subjects will be summarized by actual treatment group and visit, in the form of a shift table to detect changes from baseline. All 12-Lead ECG data will be listed for each subject by actual treatment group and visit.

12.6 Physical Examination and Weight

Physical examination findings will be classified as “Normal”, “Abnormal, NCS”, “Abnormal, CS” or “Not done” with specification. The number and percentage of subjects will be provided by actual treatment group and body system, in the form of a shift table to detect changes from baseline. The following body systems will be examined;

- Head
- Neck
- Ear and Throat
- Thorax
- Abdomen
- Extremities
- Neurological System
- Skin and Mucosae

All Physical examination data will be listed for each subject by actual treatment group, visit and body system. Weight will be summarized in the form of change from baseline table by actual treatment group, at each scheduled collection time (Baseline, Day 110/EOS) using descriptive statistics. Weight will be listed with physical examination for each subject by actual treatment group and visit.

12.7 Pregnancy Test

Females of childbearing potential will have urine pregnancy test performed at screening by a local laboratory and will have an additional test for pregnancy at the end of the study (Day 110). If the urine pregnancy test gives equivocal results, a serum pregnancy test will be performed prior to study drug administration. Subjects

Statistical Analysis Plan

with a positive test result will be excluded from the study.

Urine pregnancy results will be classified as "Positive", "Negative" or "Equivocal" and Serum pregnancy results will be "Positive" or "Negative".

The pregnancy test by urine and serum pregnancy results will be summarized in a table by actual treatment group and visit showing the number and percentage of subjects. Percentages are calculated by using the number of female of child-bearing potential in the Safety population as the denominator. All pregnancy test result will be listed for each subject by actual treatment group, visit and individual test results.

12.8 Chest X-ray

Chest X-ray assessment will be performed at screening. If symptoms have not relieved up to Day 3, chest X-ray will be performed to determine presence of secondary complications of influenza A infection. Moreover, if the investigator considers chest X-ray is necessary, then it will be performed during the study to evaluate the lower respiratory tract. Findings will be classified as "Normal", "Abnormal, NCS" or "Abnormal, CS". The number and percentage of subjects regarding the result of chest X-ray assessment will be summarized by actual treatment group and visit in the form of a shift table to detect changes from baseline.

All chest X-ray result will be listed for each subject by actual treatment group and visit.

12.9 Suspicious ADE

Subjects will be considered to possibly have ADE if they meet any of the following criteria:

- Symptoms have not resolved or have worsened up to Day 8 after the administration of study drug in the opinion of the investigator
- The subject develops a secondary influenza-like illness after Day 8

Subjects with suspicious ADE will be required to assess virus titer using the nasopharyngeal swab sample, Flu-iiQ™ and body temperature up to Day 8 after the day of ADE occurrence. If symptoms have not resolved or have worsened up to Day 8 after the day of ADE occurrence, same procedures will repeat.

The number and percentage of subjects who meet the criteria for suspicious ADE will be presented by actual treatment group.

Data recorded in 'Suspicious ADE' page of eCRF will be listed in listings for Flu-iiQ™, body temperature and virus titer of nasopharyngeal swab samples which are collected in scheduled visits.

13. Changes to Protocol-Specified Analysis

- The analysis scope for the 1st CSR is extended up to Day 110/EOS for subjects who enrolled in the first season to obtain sufficient data. (currently specified in 8.0 section of the protocol, but updated in 1.1 section of SAP)
- The definition of ITT population is changed to exclude subjects who are screening failures but randomized by accident. (currently specified in 8.4.1 section of the protocol, but updated in 5.3 section of the SAP)
- The definition of safety population is changed to include all subjects who receive any amount of study drug even if it's only the normal saline solution but to analyze such subjects as the placebo group. (currently specified in 8.4.3 section of the protocol, but updated in 5.3 section of the SAP)
- The sensitivity analysis using tipping point analysis will be performed only when there is no censoring case. (currently specified in 8.6.1 section of the protocol, but updated in 10.1 section of the SAP)
- Handling of BLQ values after administration of study drug is updated. (currently specified in 8.5.3 section of the protocol, but updated in 11.1.1 section of the SAP)
- Description of %AUCex is updated according to the European Medicines Agency's guidance in "GUIDELINE ON THE INVESTIGATION OF BIOEQUIVALENCE". (CPMP/QWP/EWP/1401/98 Rev. 1)

CONFIDENTIAL

Statistical Analysis Plan

(CHMP 2010). (currently specified in 8.5.3 section of the protocol, but updated in 11.1.2 section of the SAP)

- Sensitivity analyses of primary efficacy analysis are added.

Statistical Analysis Plan

14. Appendices

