3.2 Secondary Objectives

The secondary objective is to evaluate the additional efficacy and safety of CT-P27, including potential effects on the incidence of antibody-dependent enhancement (ADE).

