6.2.5 Antibody-dependent Enhancement

Subjects will be monitored for symptoms and levels of viral shedding suggestive of suspicious ADE throughout the study.

Subjects will be considered to possibly have ADE if they meet any of the following criteria:

- Symptoms have not resolved or have worsened up to Day 8 after the administration of study drug in the opinion of the Investigator.
- The subject develops a secondary influenza-like illness after Day 8.

Figure 4 Flow chart of Antibody-Dependent Enhancement (ADE)

If a subject meets any of the criteria for suspicious ADE, virus titer will be measured using nasopharyngeal swab samples collected at the time of occurrence, Day 2 (24 hours [± 4 hours] after the day of ADE occurrence), Day 3 (48 hours [± 4 hours] after the day of ADE occurrence), Day 5 (96 hours [± 4 hours] after the day of ADE occurrence) and Day 8 (168 hours [± 4 hours] after the day of ADE occurrence). Those subjects will need to record Flu-iiQ™ (influenza symptoms) and body temperature in their diary twice a day (at approximately 12-hour intervals) from the day of ADE occurrence to Day 8 (168 hours after the day of ADE occurrence): in the morning [between 6 and 10 AM, approximately] and in the evening [between 6 and 10 PM, approximately]. If symptoms have not resolved or have worsened up to Day 8 after the day of ADE occurrence, same procedures will repeat. In addition, genotypic analysis on HA and NA genes and phenotype characterization of potential escape variants with regard to CT-P27 will be performed.

If suspicious ADE occurs, DSMB will provide recommendations to continue or stop study after review of the case of suspicious ADE.

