2.2 Secondary Objectives

To evaluate the additional efficacy and safety of CT-P27, including potential effects on the incidence of Antibody-Dependent Enhancement (ADE)

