Evaluation	Suspicious ADE Assessment				
	Day of occurrence ¹	Day 2	Day 3	Day 5	Day 8 ⁵
Collection of a nasopharyngeal swab	X	X	X	X	X

 • Virus titer (qPCR and Cell culture)² 	x	x	x	x	x

 • The characterization of isolated influenza viruses 	x	(x)			
Flu-iiQ™ ³			X		
Body Temperature ⁴			X		

1. The day of suspicious ADE occurrence.
 - Symptoms have not resolved or have worsened up to Day 8 (168 hours) after the administration of study drug in the opinion of the Investigator.
 - The subject develops a secondary influenza-like illness after Day 8 (168 hours).
2. Nasopharyngeal swab will be collected once a day up to Day 8 on the following schedule:
 - Day of occurrence
 - Day 2: 24 hours (±4 hours)
 - Day 3: 48 hours (±4 hours)
 - Day 5: 96 hours (±4 hours)
 - Day 8: 168 hours (±4 hours)
3. Flu-iiQ™ and the body temperature in the diary twice a day up to Day 8 (168 hours) from Day 1 to Day 8 (in the morning [between 6 and 10 AM, approximately] and in the evening [between 6 and 10 PM, approximately]).
4. Body temperature will be assessed by Sponsor-supplied thermometer.
5. If symptoms have not resolved or have worsened up to Day 8 after the day of ADE occurrence, same procedure will repeat.

CONFIDENTIAL

Statistical Analysis Plan

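### The specified ADE summary pools slow recovery with possible enhancement, so a working drug can mask an ADE excess; split it by trigger and show virus status

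*SAP*

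**What the plan says.** Protocol 3.2 sets the secondary objective as further efficacy and safety, "including potential effects on the incidence of antibody-dependent enhancement (ADE"). SAP 2.2 repeats it, and Protocol 8.2.3 and SAP 3.2 list ADE evaluation among the secondary safety endpoints.

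SAP 12.9 defines a suspicious case: "Subjects will be considered to possibly have ADE if they meet any of the following criteria". There are two criteria:

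- The first concerns slow or worsening recovery: "Symptoms have not resolved or have worsened up to Day 8 after the administration of study drug in the opinion of the investigator"
- The second concerns a later episode: "The subject develops a secondary influenza-like illness after Day 8"

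Protocol 6.2.5 has the same pair. The schedule for suspicious ADE in SAP 14.1 fixes the cut-off: "Symptoms have not resolved or have worsened up to Day 8 (168 hours) after the administration of study drug". Protocol 6.2.5 says that monitoring covers viral shedding as well as symptoms, but neither criterion contains a viral measure.

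The analysis specified in SAP 12.9 is: "The number and percentage of subjects who meet the criteria for suspicious ADE will be presented by actual treatment group". Protocol 8.5.4.1 plans the same single count. Table 14.3.6 is the only ADE table in SAP 14.7. The text specifies no split by criterion, no condition on virus, and no interval or test. Flagged subjects give further swabs, questionnaires and temperatures, which SAP 12.9 assigns to listings.

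**The concern.** The first criterion is close to the primary endpoint turned round. The primary endpoint is time to resolution, and this criterion flags subjects who have not resolved by 168 hours. SAP 10.1 shows the overlap, because the primary analysis draws on diary records made during suspicious-ADE follow-up. Protocol 6.2.1.3 says that lack of efficacy is not an adverse event, yet slow recovery feeds directly into this safety count.

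A pooled count therefore moves in two directions at once. Efficacy lowers it on active treatment and enhancement raises it. If efficacy is near the planned size, the net result can favour CT-P27 while a real excess is present. SAP 1.1 says that safety information from this trial will inform dose selection for later studies, so a misleading direction would matter.

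**Working it through.** **The plan's own figure.** The documents give no expected suspicious-ADE rate and no power for ADE. The nearest stated figure is 80% power for one dose against placebo (SAP 5.2: 63 vs 38 evaluable, 1.8 days, SD 3 days, two-sided 5%, rank-sum test). With the rank-sum efficiency of 3/π, the effective sizes are 38 × 0.955 = 36.3 and 63 × 0.955 = 60.2. The standard error is 3 × √(1/36.3 + 1/60.2) = 0.631, and 1.8/0.631 = 2.85. Power is Φ(2.85 − 1.96) = 81.4%; simulation with normal data gave 80.6%. The stated figure is reproduced, so 1.8 days and SD 3 days are used below.

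**Inputs.** Cut-off: 168 hours = 7 days (SAP 14.1). Benefit 1.8 days and SD 3 days (SAP 5.2). Assumed, because the documents do not give them: placebo mean m of 4, 5 or 6 days, and a gamma shape.

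**Formulas.** A gamma distribution with mean m and SD 3 has shape (m/3)² and scale 9/m.

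- Placebo share flagged by slow recovery: p0 = P(T > 7) at mean m.
- Active share: p1 = P(T > 7) at mean m − 1.8.
- With a true ADE excess e, the active share is p1 + (1 − p1)e.
- Break-even excess, where the active share only equals placebo: (p0 − p1)/(1 − p1).

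| Assumed placebo mean | p0 | p1 | Active with e = 5% | Break-even e |
|---|---|---|---|---|
| 4 days | 14.4% | 7.1% | 11.8% | 7.8% |
| 5 days | 21.5% | 10.5% | 15.0% | 12.3% |
| 6 days | 31.5% | 15.6% | 19.8% | 18.8% |

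For the first row: (0.144 − 0.071)/(1 − 0.071) ≈ 0.078. Adding 5 points without allowing for overlap gives 12.1%, 15.5% and 20.6%, which is also below placebo.

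**Other shapes.** The check was repeated with normal, gamma and lognormal shapes and placebo means of 4 to 7 days, which makes 12 scenarios. A 5% excess was masked in all 12 and a 10% excess in 10.

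**Smaller drug effects (gamma, e = 5%, same overlap formula).**

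| Drug effect | Active vs placebo, mean 4 | Mean 5 | Mean 6 |
|---|---|---|---|
| None | 18.7 vs 14.4% | 25.4 vs 21.5% | 34.9 vs 31.5% |
| 0.5 day | 16.2 vs 14.4% | 21.7 vs 21.5% | 29.8 vs 31.5% |
| 1 day | 14.2 vs 14.4% | 18.7 vs 21.5% | 25.4 vs 31.5% |

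Masking therefore depends on efficacy. It is absent with no effect, partial at half a day, and present at means 5 and 6 with a 1-day effect (about equal at mean 4). One day is the benefit that Protocol 4.2 attributes to available treatment.

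**What a split could detect.** Suppose ADE were counted apart from slow recovery, with an assumed 1% background. A true excess of 5%, 10% or 15% in one active arm of 70 against 43 on placebo then has Fisher power of about 8%, 49% and 83%.

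**The case against.** A reader might infer that the table would look reassuring whether or not ADE occurs, or that it can never show an excess. The documents do not support that. With no drug effect, or half a day at means 4 and 5, a 5% excess puts the active count above placebo. At the full 1.8 days and mean 4, a 10% excess also shows, at 7.1 + 92.9 × 0.10 ≈ 16.4% against 14.4%. What remains is that a raised count still could not be attributed to ADE rather than to slow recovery.

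A reader might also infer that the virus titres are listed and enter no summary. That is not established. SAP 14.7 names the qPCR and culture listings as sources for Table 14.3.6, and no table shell is available to show what the table holds beyond the count. SAP 5.1 admits unscheduled results to tables when they are needed for interpretation. SAP 10.2 summarises scheduled titres to Day 8 by arm. Protocol 6.2.5 adds genotype and phenotype work and DSMB review. None of these, as specified, reports titres by ADE status and arm.

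The proxy is inexact. The trigger is the investigator's opinion of symptoms, whereas the primary endpoint also requires normal temperature and is delayed by allowances for symptom-relief drugs (SAP 10.1 and 14.5). The second trigger need not fall with efficacy, but pooling hides it. The plan calls these cases suspicious, describes them only, and does not expect ADE (Protocol 2.4.1). That limits the weight of the point but does not remove it.

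**Conclusion.** The point holds in a conditional form. The specified pooled count mixes efficacy with possible harm. If CT-P27 works near the planned 1.8 days, an ADE excess below about 8% to 19% can leave the active count below placebo, under a gamma shape, SD 3 days and an assumed placebo mean of 4 to 6 days. With little or no effect the excess is not masked, but the table cannot separate it from slow recovery. The percentages show the direction and rough size of the problem; they do not predict trigger rates. The screening trigger itself is not at issue. A clearer table is worth its small cost, though power for a small excess stays low.

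**What to change.** In SAP 12.9 and Table 14.3.6, keep the pooled total and add a descriptive split by arm:

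- (a) not resolved by Day 8, without worsening;
- (b) worsened by Day 8, taken from the eCRF if it is recorded separately there, otherwise derived from the Flu-iiQ diary by a rule fixed before unblinding;
- (c) a new influenza-like illness after Day 8.

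For each row, show how many were virus-positive by qPCR or culture at the occurrence swab, and how many had a rise in titre. For (a) and (b), the occurrence swab nearly coincides with the scheduled Day 8 swab. Compare Day 8 or occurrence with Day 5, or the later ADE swabs with Day 8. For (c), compare with the scheduled Day 8 swab.

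State that the total and row (a) are confounded with efficacy and must not alone support a conclusion on ADE incidence. Still show the row (a) cases with persistent or rising titre; dropping them would amount to a new case definition.

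Cost: one extended table from swabs and diaries already planned, with small cells and low power for a small excess. The clinical trigger and DSMB process stay as they are.

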8.6.1 Missing Data

Missing data from subjects who withdraw from the study, including AEs and any follow-up, will be included in the primary endpoint analysis in the ITTI population. Assuming Missing at Random (MAR), multiple imputation will be the primary imputation method for handling the missing data. Sensitivity analysis using tipping point analysis under Missing Not at Random (MNAR) will be also accessed for the primary endpoint analysis in the ITTI population.

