The primary efficacy endpoint will be analyzed using a Wilcoxon rank-sum test to assess differences between treatment groups (CT-P27 45 mg/kg vs placebo, CT-P27 90 mg/kg vs placebo), if every subject is followed until resolution of influenza symptoms and fever. The Wilcoxon rank-sum test will be used to test for a statistical significant difference of time to resolution between placebo and CT-P27. The results of the analysis will be summarized using p-values. The significant level will be set to 5%. If p-value is lower than 5%, it is considered that there is a significant difference between placebo and CT-P27. For subjects who withdrew from the study before the symptoms have resolved or if the symptoms did not resolve until the data cut-off, data will be censored at the latest date/time recorded on the diary or start date/time of study drug administration when there are no recorded data on the diary after study drug administration. If there is any censoring, the primary efficacy endpoint will be analyzed using Log-rank test and Gehans Wilcoxon test, and the result will be presented by p-values from the two tests. Also the table will present count of censoring reasons and 25th percentile, median, 75th percentile of time from administration of study drug to resolution. Kaplan-Meier plots will be presented.

CONFIDENTIAL

Statistical Analysis Plan

If there are no censoring data, sensitivity analysis using tipping point analysis under Missing Not at Random (MNAR) will be also performed to explain varying cases about average unobserved outcomes dropouts on two treatment groups.

Sensitivity Analyses which alter resolution conditions of primary efficacy analysis will be performed on the ITTI population. Following two endpoints will be assessed as described for the primary efficacy endpoint.

- Time (in days) to resolution of influenza symptom (respiratory and constitutional symptoms)

In the analysis, fever is not considered and the definition of resolution of symptom is the same as those of primary efficacy analysis.

- Time (in days) to resolution of influenza symptom and fever

In the analysis, threshold of resolution of fever is changed to 37.8°C and the definition of resolution of symptom is the same as those of primary efficacy analysis.

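### The SAP runs the protocol's MNAR tipping-point analysis only when no subject is censored, which is when there are no unobserved dropout outcomes to vary

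*SAP*

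**What the plan says.** Protocol 8.6.1 makes multiple imputation under missing at random (MAR) the main method for missing data and adds an MNAR check with no condition attached: "Sensitivity analysis using tipping point analysis under Missing Not at Random (MNAR) will be also accessed for the primary endpoint analysis", in the ITTI population.

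SAP 10.1 attaches a condition: "If there are no censoring data, sensitivity analysis using tipping point analysis under Missing Not at Random (MNAR) will be also performed". It gives the purpose as "to explain varying cases about average unobserved outcomes dropouts on two treatment groups". SAP Section 13 lists the restriction as a change from protocol 8.6.1: "The sensitivity analysis using tipping point analysis will be performed only when there is no censoring case". It gives no reason.

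SAP 10.1 also defines who is censored. "For subjects who withdrew from the study before the symptoms have resolved or if the symptoms did not resolve until the data cut-off", then "data will be censored at the latest date/time recorded on the diary or start date/time of study drug administration"; the second of those times applies when there is no diary entry after dosing.

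If anyone is censored, the SAP replaces the Wilcoxon rank-sum test with log-rank and Gehan tests and adds Kaplan-Meier plots. "Also the table will present count of censoring reasons and 25th percentile, median, 75th percentile of time from administration of study drug to resolution". The two new sensitivity analyses address a different question: "Sensitivity Analyses which alter resolution conditions of primary efficacy analysis will be performed on the ITTI population".

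**The concern.** A tipping-point analysis asks how bad the unseen outcomes of dropouts would have to be before the conclusion changes. It needs subjects whose outcome is unseen. Under the SAP's censoring rule those subjects are the censored ones, so requiring no censoring removes the subjects the analysis is about.

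Withdrawal before resolution may depend on how the subject is doing. Censoring assumes that those who left would have gone on to resolve like those who stayed. The planned tables and plots will show who left and when, but they do not test that assumption. A significant dose-versus-placebo result could then be reported with no prespecified statement of how much later the dropouts must resolve before significance is lost. SAP 1.1 says the effect size will inform dose selection for later studies, so the robustness of the result matters even in a proof-of-concept trial.

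**Working it through.** **1. The logic of the condition**

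| State of the data | Unobserved dropout outcomes | Tipping point under the SAP |
|---|---|---|
| No subject censored | None, since every withdrawal before resolution is censored | Runs, with nothing to vary |
| At least one subject withdrew before resolution | One or more | Off |
| Nobody withdrew, but one subject unresolved at cut-off | None from dropout, one unresolved time | Off |

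**2. Whether anything else fills the gap**

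- Log-rank and Gehan tests: both assume non-informative censoring.
- The two added sensitivity analyses: one drops fever, the other moves the fever threshold to 37.8°C. Neither concerns dropout.
- Imputation (SAP 10.3.1, approach 2): it fills Flu-iiQ items with zero or imputes them under MAR. Whether it reaches diary entries after a subject stops is unclear from rules 2-2-1 and 2-2-2. Missing diary temperature is not imputed; only a single gap between two resolved readings is bridged. It is not an MNAR check.

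**3. Chance that the condition is met**

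Inputs: 164 eligible infected subjects, 63 per dose and 38 placebo (SAP 5.2), so 63 + 38 = 101 in one comparison. The sample size reproduces: 164 / 0.90 = 182.2, rounded up to 183. Power for 63 versus 38, 1.8 days, SD 3, two-sided 5% is 81.2% by Wilcoxon simulation, against the stated 80%.

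The censoring rate *p* is an assumption. With independent subjects, P(no censoring) = (1 − p)^n.

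| p | n = 164 | n = 101 |
|---|---|---|
| 0.5% | 44% | 60% |
| 1% | 19% | 36% |
| 2% | 3.6% | 13% |
| 5% | 0.02% | 0.6% |

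The plan's 10% dropout rate is an upper reference, not an estimate of *p*, because leaving after resolution does not censor the endpoint.

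**4. Whether some censoring is likely**

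Assume gamma-distributed times with SD 3, placebo mean 5 or 6 days, and CT-P27 mean 1.8 days lower (3.2 or 4.2). P(T > 7 days) is 0.215 or 0.315 on placebo and 0.105 or 0.156 on CT-P27. Expected unresolved at 7 days:

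- 126 × 0.105 + 38 × 0.215 = 21
- 126 × 0.156 + 38 × 0.315 = 32

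The routine diary stops at Day 8 (Protocol 6.1.1). It continues only for suspicious ADE, which for non-resolution rests on the investigator's opinion (Protocol 6.2.5).

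**5. What the missing check could reveal**

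Simulation: 63 versus 38, the same gamma times on a 12-hour grid, 2,500 trials per scenario. The stated numbers of unresolved subjects drop out 1 to 3 days after dosing; everyone else is followed to resolution. The table gives the share of log-rank-significant results favouring CT-P27 that lose significance once dropouts are given their simulated time plus a delay. Ranges cover placebo means 5 and 6.

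| Dropouts (CT-P27 + placebo) | Delay applied to | No delay | 2 days | 4 days |
|---|---|---|---|---|
| 3 + 0 | CT-P27 | 2.5–3.3% | 8.5–10.4% | 20.5–23.4% |
| 6 + 0 | CT-P27 | 4.5–5.2% | 18.3–20.9% | 45.1–45.2% |
| 3 + 2 | Both arms | 4.2–4.5% | 5.9% | 8.6–9.8% |
| 6 + 4 | Both arms | 4.9–5.6% | 7.5–9.1% | 13.5–15.0% |
| 3 + 2 | CT-P27 only | 3.3–4.0% | 9.7–10.6% | 20.8–21.8% |
| 6 + 4 | CT-P27 only | 5.4–7.2% | 19.6–22.8% | 43.4–45.7% |

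The Monte Carlo standard error is about 0.4 to 1.2 points.

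**The case against.** - **The change is disclosed and permitted.** Protocol 8.3 requires changes to be documented in the SAP, and Section 13 does so. The tipping-point table (14.2.1.3) cites the same source listings as the Wilcoxon tables and omits the End of Study listing, which suggests a deliberate assignment to the uncensored branch. This stands, but neither disclosure nor intent repairs a condition that removes the subjects of the analysis, and no reason is given.
- **Imputation might leave something to vary.** If approach 2 reaches post-withdrawal diaries, a subject whose fever had already resolved could gain an imputed resolution time and count as uncensored. The text does not settle this. It would cover at most some dropouts, and the tipping point would still be off whenever any other subject stayed censored.
- **The 21 to 32 is not a censoring count.** Non-resolution at Day 8 can trigger suspicious-ADE follow-up, and SAP 10.1 uses those diary records. On the same gamma assumptions only about 1 of 164 is unresolved at 15 days (126 × 0.0066 + 38 × 0.0078 = 1.1; 126 × 0.0068 + 38 × 0.0103 = 1.3). This is fair, but one censored subject still switches the analysis off.
- **The simulation is an illustration, and its percentages are gross.** It assumes follow-up to resolution; ending the diary at 7.5 days lowers the 6 + 0, 4-day figure from about 45% to 35–36%. The no-delay column must be subtracted: for 3 + 2 with equal delays the net loss is about 1 to 5 points. A 4-day delay is large against an assumed CT-P27 mean of 3.2 to 4.2 days. All of this stands and limits the size claimed, not the fault.
- **Only a supportive analysis is lost.** True; the primary test and estimates are unaffected.

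**Conclusion.** The concern holds. The SAP turns an unconditional protocol commitment into an analysis that can run only when there is no unobserved dropout outcome for it to examine. That follows from the text and needs no assumption about rates.

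How often the check is lost depends on the censoring rate, which the documents do not give; at an assumed 2% or more the analysis has less than a 4% chance of running with 164 subjects. The consequence for the conclusion is modest if dropouts behave alike in both arms and large only if CT-P27 dropouts fare worse. Arm-specific delays would tell these cases apart. This should be fixed; it does not invalidate the primary test.

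**What to change.** In SAP 10.1 and Section 13, delete the no-censoring condition so that the tipping point is planned as in protocol 8.6.1, in a form that handles censored times. With no censoring it simply returns the primary result. One suitable form, which the protocol does not prescribe:

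1. Impute each censored subject's remaining time to resolution under MAR.
2. Add delays in prespecified steps, set separately for each arm, until the primary conclusion changes.
3. Report the delays at which it changes, for each dose against placebo.

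State also whether approach 2 in SAP 10.3.1 applies to diary entries after a subject stops, so it is clear who remains censored.

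The cost is SAP wording and modest extra programming. A tipping-point table (14.2.1.3) is already in the list of outputs. No new data are needed and the primary test does not change.
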